6.2.3 Blinding

In Phase 2, all study personnel will remain blind to treatment condition until data is locked with the exception of (a) [name], who will execute randomizations and (b) the study therapists, who will execute the interventions. The supervisors will be aware of some identifying features of individuals (e.g., first name, appearance) in the groups under their review. There is no need for unblinding procedures as the treating clinician will not be blind to condition.

6.2.4 Followup Visits (sessions 1-8)

In both Phases, the following measures will be completed between or before sessions and collected by therapists at group meetings.

- Credibility, 3-item measure adapted from Borkovec & Nau, 1972 (end of session 1 only).

- Modified Differential Emotions Scale (mDES; Fredrickson et al., 2003), daily ratings of the strongest experience of 19 specific emotions in the preceding 24 hours
- Practice diary of time spent in and reactions to daily practice
- Reactions to group, survey and interview-based methods to gather reactions to group sessions and practices.
- Within-session heart rate monitoring (pending IRB approval)

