6	
Developing Affection and Empathy: Deeper contemplation and insight into the ways in which myriad benefits are derived from countless others, along with awareness that this kindness should be repaid, enables the participant to relate to others with a deeper sense of connectedness and affection.
 
Homework: 30 minute daily meditation with journal
	
Reviewing at-home practice and next Relaxation with script: Review of at home practice, engage in progressive relaxation with script and record this week.
 
Homework: 30 minute daily relaxation with self-monitoring

7	
Realizing Wishing and Aspirational Compassion: Enhanced empathy for others, coupled with intimate awareness of their suffering and its causes, naturally gives rise to compassion: the wish for others to be free from suffering and its conditions.
	
Reviewing Homework and next Relaxation with script: Review of at home practice, engage in progressive relaxation with script and record this week.
 
Homework: 30 minute daily relaxation with self-monitoring

	Homework: 30 minute daily meditation with journal	
8	Realizing Active Compassion for Others: In the final step, the participant is guided through a meditation designed to move from simply wishing others to be free of unhappiness to actively committing to assistance in their pursuit of happiness and freedom from suffering.	Reviewing at-home practice, next Relaxation and Relapse Prevention: Review of at home practice, engage in progressive relaxation and record at home this week. Introduce relapse prevention concept.

Refinement strategies. The interventions will be refined based on participant feedback, which will be solicited on a weekly basis through a variety of measures (refer to the Measures section for more detail) as well as through direct inquiry about reactions to the group. Participants will understand the goal of refining the intervention, so will be encouraged to provide honest feedback about their experience.

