9.5 Outcomes

9.5.1 Primary Outcome

The primary outcomes of Phase 1 are participant reactions to the group (credibility, satisfaction, attendance, practice compliance, and weekly qualitative and quantitative feedback) as well as variables that reflect changes that are expected with practice of CM (positive emotion, social connectedness, self compassion). These includes: Client Satisfaction Questionnaire, credibility score, modified Differential Emotions Scale, time spent in and reactions to daily practice, reactions to group, short form of the Self Compassion Scale and Social Connectedness Scale. Refer to section 6.2 for the schedule of administration and descriptions of measures.

The primary outcome of Phase 2 is the CAPS-5, which quantifies PTSD symptomatology.

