10.3.5 Monitoring

The VA San Diego conducts annual reviews of consent forms to assure compliance. Research assistants and therapists will be trained to review all instruments for completeness before the participant leaves the appointment. [name] will review the data set for completeness at the end of each group cycle.

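### Credibility and reactions-to-group forms are collected by the treating therapist with no confidential return, so Phase 1 acceptability may be overstated by an unknown amount

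*Combined protocol and SAP*

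**What the plan says.** Section 6.2.4 sets the collection route for the weekly measures: "In both Phases, the following measures will be completed between or before sessions and collected by therapists at group meetings". The list that follows includes credibility, given as "Credibility, 3-item measure adapted from Borkovec & Nau, 1972 (end of session 1 only", and "Reactions to group, survey and interview-based methods to gather reactions to group sessions and practices". The practice diary and the mDES are on the same list.

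Section 10.3.5 adds: "Research assistants and therapists will be trained to review all instruments for completeness before the participant leaves the appointment".

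Section 9.5.1 gives these measures primary status: "The primary outcomes of Phase 1 are participant reactions to the group (credibility, satisfaction, attendance, practice compliance, and weekly qualitative and quantitative feedback".

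Section 5.1 uses them. Its table of observations and possible refinements includes low credibility and poorly received material, and published trials serve as the benchmark for poor performance. On candour it says: "Participants will understand the goal of refining the intervention, so will be encouraged to provide honest feedback about their experience".

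Section 10.1, in contrast, has trained assessors administering the study's measures and states no exception for the weekly ones.

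**The concern.** People tend to soften criticism when the person who delivered the sessions takes the form from them. Credibility is completed at the end of the first session, and the reactions survey comes up to eight times. A participant has no stated assurance that the therapist will not see the answers.

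In Phase 1 these scores help to decide what is changed. Each group's revised protocol passes to the next group until it is judged well received, and the final version goes into Phase 2. If ratings are too kind, some weak material could be left alone, and the acceptability figures reported for planning a later trial could be too favourable.

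**Working it through.** No formula applies, and the plan gives no figure to reproduce. The check sets the sections side by side.

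**Which primary instruments take this route.** Section 9.5.1 names seven Phase 1 instruments.

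| Instrument | Where collected | On the therapist-collected list? |
|---|---|---|
| Credibility | 6.2.4, session 1 | Yes |
| Reactions to group | 6.2.4, sessions 1–8 | Yes |
| Practice time and reactions (diary) | 6.2.4, sessions 1–8 | Yes |
| mDES | 6.2.4, sessions 1–8 | Yes |
| CSQ-8 | 6.2.5, final evaluation | No; collector not named |
| SCS-SF | 6.2.2 and 6.2.5 | No; collector not named |
| Social Connectedness Scale | 6.2.2 and 6.2.5 | No; collector not named |

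So 4 of 7 are collected by the therapist. Credibility and reactions are the two that judge the treatment and its sessions, and the point rests on these. The diary records practice, and the mDES records emotions.

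**How many forms.** Phase 1, about 60 people: 60 × 1 = 60 credibility forms and up to 60 × 8 = 480 reaction forms. Phase 2, about 40 people: 40 and up to 40 × 8 = 320.

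**Which refinement triggers depend on them.** The Section 5.1 table has five rows.

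- Low enrolment or few starting sessions: not dependent.
- Low credibility: rests on the credibility form.
- Poorly received material, low satisfaction, high drop-out: partly dependent, through the reactions survey.
- Poor homework compliance: rests mainly on the diary.
- Unfavourable change in emotion, connectedness or self-compassion: uses the mDES and the baseline and final scales.

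One row therefore rests on the two forms and another depends on them in part.

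**What protection is described.** Section 10.1 identifies study data by subject number. That does not hide the respondent from a therapist who takes the form at a meeting of 6 to 12 people. No section describes sealed return, collection of these forms by someone else, or a promise that individual answers are kept from the therapist.

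**What the other channels cover.**

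- Recordings of every session are reviewed (Sections 5.1 and 10.3.1). They show behaviour in the room, not privately held doubts.
- Attendance and drop-out are not self-ratings. They do not show which material failed.
- The CSQ-8 is given once, after session 8, so it cannot point to a session.
- Qualitative interviews take place during and after treatment. The interviewer's name is removed from the public copy, so independence from the therapist cannot be judged here.

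**Consistency on staff roles.** Sections 6.2.4 and 10.1 differ on who handles the measures. The Randomization paragraph of Section 3 has an unblinded project coordinator holding the assignment list. Section 6.2.3 excepts only the person executing randomization and the therapists from blinding. This matters for the remedy, because reaction forms can reveal the arm.

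**The case against.** The strongest reply is that this is a developmental study, and its refinement decisions do not hang on these forms alone. Changes are agreed by consensus with an outside team that reviews the recordings. Participants know that criticism is wanted. Most weekly forms are completed away from the session. Quick feedback to the therapist is part of the design. All of this stands, and it limits the harm. It does not protect the scores themselves, which are primary outcomes.

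Some stronger readings are tempting, and the documents do not support them.

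- A reader might infer that acceptability **is** inflated and problems **are** hidden. The documents support only a risk, and problems can surface through the other channels.
- A reader might infer that the therapist studies each identified rating in front of the participant. Section 10.3.5 describes a completeness check, shared with research assistants.
- A reader might see every therapist-collected form as a rating of the therapist. Credibility concerns the treatment and the diary concerns practice; only the reactions survey comes near rating delivery.
- A reader might expect different bias by arm in Phase 2 because practice demands differ. The Section 5.1 tables assign the same daily minutes to both arms in weeks 1 to 7 (5, 10, 20, 20, 30, 30, 30).
- A reader might size the problem by assuming a shift in standard deviations. Concluding that such a shift would mask a deficit of equal size only restates the assumption, and the plan gives no numeric threshold.

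The reply also bears on the remedy. Homework review is session content in the relaxation arm, so taking the diary away from the therapist could alter delivery.

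**Conclusion.** The point holds as a risk of unknown size and direction most likely favourable to the intervention. It concerns two of the seven named Phase 1 primary instruments and about 60 participants. It rests on two assumptions: that the collection route is as Section 6.2.4 describes, and that participants give kinder answers when the therapist collects the form. The second is plausible but is not quantified in the documents.

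Phase 2 is less affected. Its primary outcome is the CAPS-5, rated by a blinded assessor, and neither credibility nor reactions is listed among its primary or secondary outcomes. The same route still applies to the feasibility data gathered there. The change is worth making because it costs little and protects measures that steer the refinement.

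**What to change.** - In Sections 6.2.4 and 10.3.5, have the credibility form and the reactions-to-group survey returned in sealed, ID-only envelopes. Staff other than the therapist open them and check completeness.
- Tell participants that the therapist will not see individual answers.
- Give the therapist and supervisors a de-identified group summary in time for the weekly refinement meeting.
- In Phase 2, let only the unblinded coordinator named in Section 3 open these forms, never the blinded assessor. Amend Section 6.2.3 so that its list of unblinded staff agrees. Sections 4.3 and 6.2.1 mention a combined assessor/coordinator role for consent, so state that the two roles are held by different people in Phase 2.
- Reconcile Section 6.2.4 with Section 10.1 on who administers and who collects each measure.
- Leave the practice diary available for homework review, and report practice time as self-report seen by the therapist. Leave the weekly safety measures as they are.

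Cost: envelopes, a few sentences of text and slightly more work for the coordinator. A missing item on the two forms can no longer be queried on the spot.

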6.2.5 Completion/Final Evaluation (after session 8)

The final evaluation will be completed within 1 week after completion of session 8.

Phase 1:

- Short form of the Self Compassion Scale (SCS-SF; Raes, Pommier, Neff, & Gucht, 2011), 12 items
- Social Connectedness Scale – Revised (SCS-R; Lee, Draper & Lee, 2001), 20 items
- Client Satisfaction Questionnaire (CSQ-8; Attkisson & Greenfield, 1994), 8-items
- Emory Treatment Resistance Interview for PTSD (ETRIP; phenxtoolkit.org)
- Heart rate monitoring

Phase 2:

- Brief Symptom Inventory (BSI; Derogatis, 1983), 53 items
- Clinician Administered PTSD Scale for DSM-5 (CAPS-5; Weathers et al., 2013), 45-60 minute clinician-rated measure referencing the baseline LEC and post-treatment LEC for trauma during participation
- Philadelphia Mindfulness Scale (PMS; Cardaciutto, Herbert, Forman, Moitra, & Farrow, 2008), 20 items
- PROMIS measures of pain intensity, pain interference, sleep disturbance and sleep-related impairment
- Short form of the Self Compassion Scale (SCS-SF; Raes, Pommier, Neff, & Gucht, 2011), 12 items
- Social Connectedness Scale – Revised (SCS-R; Lee, Draper & Lee, 2001), 20 items
- Sheehan Disability Scale (SDS; Sheehan, Harnett-Sheehan, & Raj, 1996), 3 items
- Satisfaction with Life Scale (SWLS; Diener, Emmons, Larsen, & Griffin, 1985), 5 items
- Emory Treatment Resistance Interview for PTSD (ETRIP; phenxtoolkit.org)
- Client Satisfaction Questionnaire (CSQ-8; Attkisson & Greenfield, 1994), 8-items
- Heart rate monitoring

For participants who terminate treatment early, we will make every effort to get them to complete the post-treatment measures. Early termination would most commonly occur because a participant stops attending groups but could also be based on clinical judgment that termination would be in the participant's best interest. This information is an important part of the feasibility of this study.

7. SAFETY ASSESSMENTS

At the eligibility assessment and other assessments for enrolled subjects, the interview questions and/or questionnaires may produce distress or discomfort from the discussion of personal, emotional, or anxiety-provoking topics. Assessors will be trained to identify signs of such distress and to engage a licensed clinician if it should occur.

Meditation and relaxation have been evaluated in prior studies with patients with PTSD, and have been shown to be safe and well-tolerated. It is unlikely but possible that some distress will arise during the intervention. In particular, it is possible that sitting quietly with one's internal experience during meditation practice, having compassion for oneself (in cases where guilt and shame predominate), or trying to wish a perpetrator to be free of suffering will be emotionally challenging for people with PTSD. The likelihood of such distress is equal to or less than that associated with current empirically supported treatments for PTSD, which typically involve disclosure of the traumatic event or challenge difficult beliefs about the event(s).

The course of PTSD is often characterized by fluctuations in symptoms, particularly based on reminders of traumatic experiences. Thus, it is possible that significant exacerbations of PTSD symptoms will occur during the course of treatment. Exacerbations of co-occurring conditions, including depression or suicidality, alcohol or substance use or dissociation, are also possible. As has been demonstrated previously, significant exacerbation of symptoms during psychotherapeutic treatment of PTSD is relatively rare and has no impact on rates of attrition or improvement (Foa et al., 2002). In order to monitor such changes, the following measures will be administered on a weekly basis.

- Alcohol Use Disorders Identification Test (Saunders, Aasland, Babor, de la Fuente, & Grant, 1988) consumption questions (AUDIT-C), 3 items
- Patient Health Questionnaire, depression items (PHQ-9; Spitzer, Kroenke, & Williams, 1999), 9-item self-report depression scale, anchored to the past week
- PTSD Checklist for DSM-5 (PCL-5; Weathers et al., 2013), 20 items, anchored to the past week

Rates of suicidality and homicidality are elevated in individuals with depression and PTSD. Suicidality will be evaluated weekly through the PHQ-9. Both suicidality and homicidality will be monitored by therapists, who will receive additional training in management of these issues, including introduction to site-specific procedures and resources. [name] will be notified immediately about high risk patients (e.g., cannot establish a plan with their therapist to assure their safety, hospitalization required).

Thus the possible adverse events (AEs) during both of these interventions include:

- Alcohol use
- Anxiety
- Depression
- Discomfort
- Dissociation
- Homicidality
- Substance use
- Suicidality

If an AE occurs, the therapist, in consultation with [name], will decide what measures are needed to manage the problem. Referrals for additional services will be provided as necessary.

7.1 Specification of Safety Parameters

Distress will be identified by a clinically significant increase in total score on the AUDIT, PHQ-9 or PCL or by increases on specific items, such as PHQ item 9 which queries suicidality.

At each contact with the participant, the assessor or therapist will seek information on AEs by specific questioning. Information on all AEs will be recorded immediately in the study records and VA CPRS. All AEs occurring during the study period will be recorded on AE forms.

The clinical course of each event will be followed until resolution, stabilization, or until it has been determined that the study treatment or participation is not the cause.

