6. STUDY PROCEDURES

6.1 Schedule of Evaluations

Phase 1.

	Baseline	Session 1	Session 2	Session 3	Session 4	Session 5	Session 6	Session 7	Session 8	Post-treatment
Demographics	X									
MoCA	X									
MINI	X									
DES	X									
Emory Treatment Resistance Interview for PTSD (ETRIP)	X									X
Credibility		X								
SCS-R	X									X
SCS-SF	X									X
Reactions to group		X	X	X	X	X	X	X	X	
CSQ-8										X
Practice Diary		X	X	X	X	X	X	X	X	
mDES		X	X	X	X	X	X	X	X	
LEC-5/PCL-5		X	X	X	X	X	X	X	X	
PHQ-9		X	X	X	X	X	X	X	X	
AUDIT-C		X	X	X	X	X	X	X	X	
HRV	X 72 hr	X	X	X	X	X	X	X	X	X 72 hr

Phase 2

	Screening /Baseline	Session 1	Session 2	Session 3	Session 4	Session 5	Session 6	Session 7	Session 8	Post-treatment
Demographics	X									
MoCA	X									
MINI	X									
DES	X									
Emory Treatment Resistance Interview for PTSD (ETRIP)										X
CAPS-5	X									X
BSI	X									X
SDS	X									X
SWLS	X									X
PHLMS	X									X
SCS-R	X									X
SCS-SF	X									X
PROMIS pain	X									X
PROMIS sleep	X									X
Credibility		X								
Reactions to group		X	X	X	X	X	X	X	X	
Practice Diary		X	X	X	X	X	X	X	X	
CSQ-8										X
mDES		X	X	X	X	X	X	X	X	
PCL-5		X	X	X	X	X	X	X	X	
PHQ-9		X	X	X	X	X	X	X	X	
AUDIT-C		X	X	X	X	X	X	X	X	
HRV	X 72 hr	X	X	X	X	X	X	X	X	X 72 hr

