6.2.2 Enrollment, Baseline, and/or Randomization

Enrollment is defined as the date all of the screening criteria are met and the individual agrees to participate (typically the screening/baseline visit).

Baseline Assessments

Phase 1:

- Short form of the Self Compassion Scale (SCS-SF; Raes, Pommier, Neff, & Gucht, 2011), 12 items
- Social Connectedness Scale – Revised (SCS-R; Lee, Draper & Lee, 2001), 20 items
- Heart rate monitoring

Phase 2:

- Brief Symptom Inventory (BSI; Derogatis, 1983), 53 items
- Clinician Administered PTSD Scale for DSM-5 (CAPS-5; Weathers et al., 2013), 45-60 minute clinician-rated measure referencing the Life Events Checklist (LEC) for lifetime trauma
- Philadelphia Mindfulness Scale (PHLMS; Cardaciotto, Herbert, Forman, Moitra, & Farrow, 2008), 20 items
- PROMIS measures of pain intensity, pain interference, sleep disturbance and sleep-related impairment
- Short form of the Self Compassion Scale (SCS-SF; Raes, Pommier, Neff, & Gucht, 2011), 12 items
- Social Connectedness Scale – Revised (SCS-R; Lee, Draper & Lee, 2001), 20 items
- Sheehan Disability Scale (SDS; Sheehan, Harnett-Sheehan, & Raj, 1996), 3 items
- Satisfaction with Life Scale (SWLS; Diener, Emmons, Larsen, & Griffin, 1985), 5 items
- Heart rate monitoring

Randomization

Phase 2 randomization will occur within 1 month of baseline assessment and within 1 week of the beginning of treatment groups.

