9.5.2 Secondary Outcomes

The secondary outcomes of Phase 1 are the rate of study enrollment based on various types of recruitment strategies as well as gender.

The secondary outcomes of Phase 2 include symptoms that frequently co-occur with PTSD (Brief Symptom Inventory, PROMIS measures of pain intensity, pain interference, sleep disturbance and sleep-related impairment), functioning/quality of life (Sheehan Disability Scale and Satisfaction with Life) as well as variables that capture the mechanisms by which CM may create change, including positive emotion (modified Differential Emotions Scale), social connectedness (Social Connectedness Scale), self-compassion (Short form of the Self Compassion Scale) and mindfulness (Philadelphia Mindfulness Scale).

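### Positive emotion (mDES) has no scheduled pre-treatment rating, and in Phase 2 no pre-randomisation rating; the weekly symptom scales share the gap with smaller consequences

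*Combined protocol and SAP*

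**What the plan says.** The Phase 2 rows in Section 6.1 read "mDES X X X X X X X X", "PCL-5 X X X X X X X X" and "PHQ-9 X X X X X X X X". The eight marks stand under sessions 1 to 8. AUDIT-C has the same pattern, and so do the Phase 1 rows, where PCL-5 appears as LEC-5/PCL-5. The baseline list (6.2.2) and the final-evaluation list (6.2.5) also omit all four scales.

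On timing, "Phase 2 randomization will occur within 1 month of baseline assessment and within 1 week of the beginning of treatment groups" (6.2.2). The Précis puts baseline evaluation within a month of the start of the groups. Section 5.2 says patients cannot be blinded.

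For a list that includes mDES, but not PCL-5, PHQ-9 or AUDIT-C, Section 6.2.4 says "the following measures will be completed between or before sessions and collected by therapists at group meetings". It describes mDES as a daily rating of the last 24 hours. Section 7 gives the other three weekly, with PHQ-9 and PCL-5 covering the past week.

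Section 9.1 frames positive emotion as a change outcome in Phase 1, and 9.5.1 lists mDES among the Phase 1 primary outcomes. In Phase 2 the secondary outcomes cover mechanisms, "including positive emotion (modified Differential Emotions Scale" among them (9.5.2).

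On safety, Section 7.1 states "Distress will be identified by a clinically significant increase in total score on the AUDIT, PHQ-9 or PCL", and Section 7.3 defines an adverse event by comparison with baseline. For early terminators, Section 6.2.5 says "we will make every effort to get them to complete the post-treatment measures", while Section 8 has them asked for every assessment still outstanding.

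**The concern.** A change score needs a starting value that the treatment, and knowledge of the assigned treatment, cannot have influenced. Section 9.1 names three processes that compassion meditation is expected to change: positive emotion, social connectedness and self-compassion. The plan takes the last two (SCS-R, SCS-SF) at baseline and post-treatment. Positive emotion is the exception, and no reason is given.

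If the first mDES rating already reflects expectation about the assigned arm, or the first days of practice, change measured from it can be distorted. In Phase 2 the distortion can differ between arms. Positive emotion is also a hypothesised mechanism (2.2), and little change in it is one of the observations that can prompt refinement of the intervention (5.1). A study meant to supply parameters for later efficacy trials (1.1) would therefore lack a clean starting value for it.

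The safety wording has a milder form of the same problem: it speaks of an increase, and of baseline, on scales that are not collected at baseline.

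**Working it through.** **1. Count of scheduled scores (6.1, same in both phases)**

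| Scale | Baseline | Sessions 1–8 | Post-treatment |
|---|---|---|---|
| mDES | 0 of 1 | 8 of 8 | 0 of 1 |
| PCL-5 | 0 of 1 | 8 of 8 | 0 of 1 |
| PHQ-9 | 0 of 1 | 8 of 8 | 0 of 1 |
| AUDIT-C | 0 of 1 | 8 of 8 | 0 of 1 |
| SCS-SF, SCS-R | 1 of 1 | 0 of 8 | 1 of 1 |

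The lists in 6.2.2 and 6.2.5 agree with the table, so a column shift in the extracted text does not explain the pattern.

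**2. Position of the first mDES rating**

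The Phase 2 order is baseline visit, randomisation (up to a week before the groups start), session 1. The scheduled number of pre-randomisation mDES ratings is therefore 0. Phase 1 is not randomised (Section 3), so there the gap is only that no pre-treatment rating is scheduled.

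The plan does not say when the first mDES form is issued. If it is handed out before session 1, the first ratings describe days before treatment. If it is handed out at session 1, they describe days after treatment began. Section 6.2.4 permits either.

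**3. Safety scales**

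A PCL-5 or PHQ-9 form completed at session 1 mostly describes the preceding week, and later forms can be compared with it or with the week before. Change in the interval of up to a month between baseline and session 1 cannot be seen on these scales. Phase 2 has pre-randomisation CAPS-5 and BSI scores; Phase 1 has neither, so PCL-5 is its only PTSD severity scale.

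**4. Early leavers**

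The measures that 6.2.5 seeks exclude all four scales. Section 8, read literally, includes the remaining weekly forms. Section 6.2.4 has mDES collected at group meetings, and no route is described for someone who no longer attends. Values up to the point of leaving remain available.

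**5. Precision in Phase 2 (illustrative)**

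The plan gives no power, effect size or correlation, so there is no figure of its own to reproduce. About 40 participants in 1:1 allocation is 20 per arm; four groups of 6 to 12 give 12 to 24 per arm. The 95% half-width of a standardised difference is

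- without a covariate: t(0.975, 2n − 2) × √(2/n)
- with a baseline covariate: t(0.975, 2n − 3) × √(2/n) × √(1 − r²)

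For n = 20, √(2/20) = 0.316. The unadjusted value is 2.024 × 0.316 = 0.640. With r = 0.5 it is 2.026 × 0.316 × 0.866 = 0.555.

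| n per arm | No covariate | r = 0.3 | r = 0.5 | r = 0.7 |
|---|---|---|---|---|
| 12 | 0.847 | 0.810 | 0.735 | 0.606 |
| 20 | 0.640 | 0.611 | 0.555 | 0.458 |
| 24 | 0.581 | 0.555 | 0.504 | 0.415 |

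The values of r are assumed, and participants are treated as independent within therapy groups. The comparator is no covariate. A session 1 score could also be used for adjustment, so the gain over that is smaller; it was not computed.

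**The case against.** The strongest reply is that session 1 is close enough to a baseline. PCL-5 and PHQ-9 look back a week, detecting worsening within a person needs an earlier score rather than a pre-randomisation one, and Sections 7 and 7.1 add item-level increases, questioning about adverse events at each contact and therapist monitoring. For the safety scales most of this stands. A reader might infer that the rule for an increase has nothing to compare against; the documents do not support that. For mDES the reply is weaker: the 24-hour window gives no week of look-back, and in Phase 2 the rating is post-randomisation whenever the form is issued for session 1.

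A reader might also infer that anyone who drops out has no end value, or that the intent-to-treat statement (9.3) is defeated. Section 8 asks early leavers for their remaining assessments, earlier values are kept, and 9.6 plans mixed-effects and pattern-mixture analyses. What stands is a difference in scope between 6.2.5 and 8, and the lack of a described collection route.

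Three further limits are fair. PCL-5, PHQ-9 and AUDIT-C are not listed as efficacy outcomes in 9.5. Section 9.6 does not name mDES among the scales compared by analysis of variance. And 9.1 describes the study as developmental, with the Phase 2 primary outcome, CAPS-5, properly measured at baseline.

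**Conclusion.** The concern holds in a limited form. No pre-treatment mDES rating is scheduled in either phase, and in Phase 2 none before randomisation, although change in positive emotion is a Phase 1 primary outcome and mDES a Phase 2 secondary outcome. This part rests on the schedule alone. Whether the first ratings also describe days after treatment began depends on when forms are issued, which the plan leaves open.

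For the three safety scales the consequence is small: deterioration between enrolment and session 1 is invisible on them, and 7.1 and 7.3 refer to a starting value the schedule does not collect. For completers, the missing post-treatment mark costs little, because session 8 falls within a week of the final evaluation.

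The precision figures (0.640 to 0.555 or 0.458 SD at 20 per arm) depend on assumed correlations and overstate the gain over a session 1 covariate. The main reason to act is a starting value free of allocation and treatment, obtained at low cost.

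**What to change.** - **mDES:** add it to the Screening/Baseline and Post-treatment columns in both phases. A few daily ratings, completed before randomisation in Phase 2 and before session 1 in Phase 1, would suit its daily format better than one rating at a visit. Use the pre-randomisation value as the covariate when mDES is compared between arms in Phase 2.
- **PCL-5, PHQ-9 and AUDIT-C:** add them to the same two visits, so that Sections 7.1 and 7.3 have a baseline value to refer to. Section 7.1 should also say which score an increase is judged against; the clinical threshold is for the investigators to set.
- **Early leavers:** reconcile Sections 6.2.5 and 8 on what is sought, and describe how forms are returned by someone who no longer attends.

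The cost is a schedule amendment. The three safety scales come to 20 + 9 + 3 = 32 items, or 51 with the 19 mDES emotions, which means a few minutes of self-report (assumed) at visits that already take place. Daily mDES ratings would also need take-home forms.
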